A change in the value of a safety laboratory evaluation can represent an AE if the change is clinically relevant (as determined by the Investigator) or if, during treatment with B-VEC, a shift of a parameter is observed from a normal value to a pathological value, or a further worsening of an already pathological value. When evaluating such changes, the extent of deviation from the reference range, the duration until return to the reference range, either while continuing treatment or after the end of treatment with B-VEC, and the range of variation of the respective parameter within its reference range, should be taken into consideration. The Investigator should decide, based on the above criteria and the clinical condition of a subject, whether a change in a laboratory parameter represents an AE. For pathological laboratory values that were not present at baseline, follow-up laboratory evaluations should be performed until the values return to within reference range or until a plausible explanation is found.

AEs should be recorded after the initial IP application through SFU/ET. AEs are to be recorded on the appropriate AE pages in the CRF and in source documents. Where possible, all AEs should be followed to resolution, or an outcome is reached.

Medical tests and examinations are performed, as appropriate, to document resolution of event(s). Where applicable and/or possible, AEs should be recorded as target wound specific.

Adverse events will be graded according to the National Cancer Institute's (NCI's) Common Terminology Criteria for Adverse Events (CTCAE) version 5.0 as applicable.

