### **8.8 Safety Analyses**

The safety and tolerability of B-VEC based on the assessment of adverse events, physical examinations, vital signs, and clinical laboratory test results. All safety analysis results will be performed using the safety population.

Adverse events will be coded using the version of MedDRA System Organ Class and Preferred Term available at the start of the trial. Adverse events will be grouped into treatment-emergent adverse events and post-treatment adverse events and will be tabulated by preferred terminology and by body system. Each AE will be counted once for each subject unless it resolves and recurs, in which case it may appear as multiple AEs. Severity, frequency, and relationship of AEs to study intervention will be presented by System Organ Class (SOC) and preferred term. Incidence of target-wound-related adverse events will be summarized by treatment, respectively, for each wound pair.

Listings will be provided for discontinuations, deviations, compliance, AEs leading to discontinuation, and target-wound-related adverse events. AE listings will include severity and relationship to study medication, as well as actions taken.

Tables will be provided summarizing reasons for premature discontinuation, protocol deviations, subject compliance, treatment-emergent AEs (TEAEs), TEAEs of target wound, TEAEs by severity, SAEs, and TEAEs leading to discontinuation.

The prior and concomitant medications will be summarized and listed by treatment. Medications will be coded with WHO Drug and categorized as either prior medications (any medication that was started before the first application of B-VEC) or concomitant medications (medication continued or newly started on or after the date of first application of B-VEC).

Medical/procedural history data collected during Screening or Visit 1 (Week 1), will be summarized by MedDRA System Organ Class and Preferred Term.

Descriptive summary of physical examinations, vital signs, and clinical laboratory tests will be reported along with data listings.

Evaluations of viral shedding, infectivity, COL7 and HSV antibodies will be done descriptively.

Any abnormal lab tests obtained during the study will be listed for individual subjects. Any positive findings of the pregnancy test will be listed.

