The number and percentage of subjects reporting a TEAE will be tabulated by system organ class and preferred term; by system organ class, preferred term, and severity (mild, moderate, and severe); and by system organ class, preferred term, and relationship (unrelated or related to treatment). The incidence of TEAEs will be summarized by preferred term, sorted by decreasing frequency in the B-VEC group, for all TEAEs, related TEAEs, serious TEAEs, and TEAEs leading to study drug discontinuation. The number and percentage of subjects reporting a TEAE of wound site reaction (based on the MedDRA higher level term) will be tabulated, preferred term and severity (mild, moderate, and severe). The incidence of serious TEAEs, TEAEs leading to premature discontinuation of treatment dose, and TEAEs leading to a dose interruption of treatment dose will be summarized by system organ class and preferred term. For all analyses of TEAEs, if the same AE (based on preferred term) is reported for the same subject more than once, the AE is counted only once for that preferred term and at the highest severity and strongest relationship to treatment.

In addition, all AEs (including non-TEAEs), serious TEAEs, TEAEs leading to discontinuation of treatment, and TEAEs leading to dose interruption of treatment will be provided in listings, study site, subject, verbatim term, MedDRA system organ class and preferred term, start and end date, seriousness, severity, relationship to the treatment, action taken with treatment and outcome.

Immune response adverse events due to a severe immune response determined by the Investigator to be possibly, probably or definitely related to B-VEC will be summarized by the number and percentage reporting such AEs along with a subject listing.

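### The SAP's once-per-subject counting rule for TEAEs has no wound-level counterpart, so the protocol's by-treatment table of target-wound events could lose a reaction that occurs on both primary wounds

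*SAP*

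**What the plan says.** SAP section 8.1 gives one counting rule and applies it to every TEAE analysis: "if the same AE (based on preferred term) is reported for the same subject more than once, the AE is counted only once for that" term. It goes on to say what is kept: "the AE is counted only once for that preferred term and at the highest severity and strongest relationship to treatment". The unit is the subject crossed with the preferred term. Neither wound nor wound treatment is mentioned.

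The one local-reaction table in SAP 8.1 is also at subject level: "The number and percentage of subjects reporting a TEAE of wound site reaction (based on the MedDRA higher level term) will be tabulated", by preferred term and severity, with no stated split by wound. Yet the same section has incidence tables "sorted by decreasing frequency in the B-VEC group", so treatment columns are assumed in a trial where each randomised subject is assigned both treatments.

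The protocol works partly at wound level. Section 6.5.1 says: "Where applicable and/or possible, AEs should be recorded as target wound specific". Section 8.8 says: "Incidence of target-wound-related adverse events will be summarized by treatment, respectively, for each wound pair", and lists a table of target-wound TEAEs. Its own counting sentence is again per subject, with an allowance for recurrence: "Each AE will be counted once for each subject unless it resolves and recurs, in which case it may appear as multiple AEs".

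**The concern.** Counting a preferred term once per subject is normal when each subject has one treatment. Here the randomisation is within the subject, so a subject with the same reaction on both primary wounds should appear once under B-VEC and once under placebo. A rule that de-duplicates by subject and claims every TEAE analysis leaves one record for the two wounds and does not say which column receives it.

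Severity and causality can also be mixed. Suppose pruritus is mild and related on the B-VEC wound, and severe and unrelated on the placebo wound. The literal rule yields one pruritus entry, severe in the severity table and related in the relationship table. Neither wound had an event that was both.

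At stake is the local-safety comparison within the primary pair. It is the only randomised, placebo-controlled one in the trial, because the secondary wounds receive open-label B-VEC.

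**Working it through.** The plan states no adverse event rate or count, so there is no figure to reproduce. The check is a comparison of texts followed by an illustration.

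**Texts side by side**

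- Scope: SAP 8.1 applies its rule to all TEAE analyses and exempts no wound-level table.
- Design: SAP 3.1.4.1 assigns one primary wound to B-VEC and the other to placebo in each subject.
- Required output: Protocol 8.8 asks for target-wound incidence by treatment within each pair. SAP 8.1 does not repeat this.
- Counting unit for that output: neither document gives one. The protocol's counting sentence is also per subject.
- Recurrence: Protocol 8.8 allows an event that resolves and recurs to appear more than once. SAP 8.1 counts it once.
- Listings: SAP 8.1 lists all AEs, but the columns it names include neither a wound identifier nor a wound treatment.

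**Illustration**

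Inputs: N = 24 pairs (SAP 3.1.3). The rate p of a given preferred term on each primary wound, equal for both wounds, and the within-subject correlation r are assumptions.

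- Probability that both wounds react: P(both) = p² + r·p(1 − p)
- Correct expected count per column: N·p
- Correct total over the two columns: 2N·p
- Total under the literal rule: N·(2p − P(both))
- Share of counts lost: P(both)/(2p)

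At p = 0.20, each column should show 24 × 0.20 = 4.8, a total of 9.6. With r = 0, P(both) = 0.04, so 24 × 0.04 = 0.96 counts are lost. With r = 1, P(both) = 0.20, so 24 × 0.20 = 4.8 are lost.

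| r | P(both) | Counts lost | Total kept, of 9.6 | Share lost | Other column if every shared record goes to one column |
|---|---|---|---|---|---|
| 0 | 0.040 | 0.96 | 8.64 | 10% | 3.84 |
| 0.3 | 0.088 | 2.11 | 7.49 | 22% | 2.69 |
| 0.6 | 0.136 | 3.26 | 6.34 | 34% | 1.54 |
| 1 | 0.200 | 4.80 | 4.80 | 50% | 0 |

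Over p from 5% to 40% and r from 0 to 1, the share lost runs from 2.5% (p = 5%, r = 0) to 50% (r = 1, any p).

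The effect on the comparison depends on where the single record goes, which the documents do not say. If shared records were split evenly, both columns would fall alike; at r = 0, each would be 4.8 − 0.96/2 = 4.32, and with equal true rates the difference would stay zero. If all went to one column, a difference would appear where none exists: 4.8 against 3.84 at r = 0.

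**The case against.** The tables that SAP 8.1 describes are counts of subjects, and there the rule is correct. The by-treatment wound table is only in the protocol, and nothing says it will be built under a literal reading of the SAP rule. A reader might infer that the comparison is already miscounted; the documents do not support that.

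The reference to a B-VEC group also permits a benign reading, in which a term counts once within each treatment column. On that reading nothing is lost from the primary pair. It is possible, but it is not stated.

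A reader might further infer that events on up to four secondary wounds would absorb primary-wound events and make the loss much larger. This is not supported either. The protocol's summary is by wound pair and secondary wounds are unmatched. Four is a maximum limited by the Remaining Weekly Dose, and any such figure needs an invented rule for which record is kept.

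Nor does an event vanish from the data. All AEs are listed, Protocol 8.8 plans a listing of target-wound-related events, and SAP 5.1 promises listings of all eCRF data. With about 24 subjects these can be read in full. The remaining gap is that the AE listing columns named in either document do not include the wound.

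Finally, wound-specific recording is asked for only where applicable or possible, and no hypothesis test is attached to the AE tables.

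What stands is narrower. The SAP's only counting rule claims all TEAE analyses, a table the protocol requires needs a different unit, and the SAP supplies neither the table nor the unit.

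**Conclusion.** The point holds as a conditional one. SAP 8.1 omits the protocol's target-wound summary by treatment, and its one counting rule, taken literally, would give a wrong count there whenever both primary wounds show the same term. It could also combine one wound's severity with the other's causality.

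Under an assumed 20% rate per wound in 24 pairs, the loss is about 1 of 9.6 expected counts with independent wounds and 4.8 of 9.6 with full correlation. Both the rate and the correlation are assumptions, so these figures show scale and do not predict a result. The size for the B-VEC versus placebo difference cannot be stated, because the documents do not say which column would keep the record.

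The differing treatment of recurrent events in the two documents needs reconciling in any case. The primary and key secondary analyses are untouched. This is worth correcting before database lock because it concerns the only randomised local-safety contrast and the correction is small.

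**What to change.** In SAP 8.1:

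1. Limit the once-per-subject rule to subject-level tables.
2. Add the protocol's target-wound TEAE table. Count each preferred term once per subject within each wound treatment, at the worst severity and closest causal rating seen on that wound. Show primary B-VEC, primary placebo and open-label secondary wounds separately.
3. Add the wound identifier and wound treatment to the AE listing columns. Because wound-specific recording is only asked for where possible, show events with no wound recorded on their own line.
4. Align the rule with Protocol 8.8 on events that resolve and recur, so that both documents say whether a recurrence adds to a count.

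The cost is SAP wording and one additional set of tables. No extra patients are needed, and no data beyond the wound-specific recording that Protocol 6.5.1 already requests.

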8.2 Vital Signs

Vital sign measurements include systolic and diastolic blood pressure, pulse, and respiratory rate as well as temperature. Vital signs data is collected during Visit 1, 5, 9, 13, 17, 21, 25 and at the safety follow-up (SFU)/ET.

Descriptive statistics of the absolute and change from baseline to each post-baseline time point values will be provided. Baseline is defined as the value closest to but prior to the initiation of treatment administration.

8.3 Physical/Skin Examination

Physical examination data is collected at Visit 1, Week 26, and safety follow-up (SFU)/ET. A full physical examination will be completed at Visit 1 (Week 1) of the body systems is included in the physical/skin examination:

- General appearance
- HEENT (Head, Ears, Eyes, Nose, Throat)
- Respiratory
- Abdomen
- Musculoskeletal
- Skin
- Spine/Neck/Thyroid
- Cardiovascular
- Nervous System

Abbreviated Physical exams will be completed at Week 26, and the safety follow-up (SFU)/ET. Subsequent abbreviated exams will be compared to the baseline exam for abnormalities.

Subject listings of all physical examination results by body system will be provided. Physical examination results will be coded using MedDRA (version to be delineated in the CSR). Any abnormalities or changes in severity noted during the exam will be provided in a subject listing.

8.4 Laboratory Values

Laboratory data is collected during Screening or Visit 1 (Week 1), and Week 26. Reference ranges are used to assess the laboratory data for clinical significance. Abnormal laboratory values which are unexpected or not explained by the subject’s clinical condition should be repeated as feasible until confirmed, explained, or resolved. Changes from baseline are recorded as an AE if deemed clinically significant by the Investigator or qualified designee.

The following evaluations are conducted:

CMP14+ DBili	CBC With Differential/ Platelet
Glucose	White blood cells (WBC)
Blood Urea Nitrogen (BUN)	Red blood cells (RBC)
Creatinine	Hemoglobin
Sodium	Hematocrit
Potassium	Mean Corpuscular Volume (MCV)
Chloride	Mean Corpuscular Hemoglobin (MCH)
Carbon Dioxide	Mean Corpuscular Hemoglobin Concentration (MCHC)
Calcium	Red Cell Distribution Width (RDW)
Protein, Total	Platelets
Albumin	Neutrophils
Bilirubin, Total	Lymphocytes
Bilirubin, Direct	Monocytes
Bilirubin, Indirect	Eosinophils
Alkaline Phosphatase	Basophils
Aspartate Aminotransferase (AST)	
Alanine Aminotransferase (ALT)	

Detailed subject listings of all laboratory data collected during the study will be provided. Laboratory values outside normal limits will be identified in the subject data listings with flags for low (L) and high (H). Actual and change from baseline laboratory values for hematology and serum chemistry will be summarized.

Data from the following other laboratory evaluations will be provided in subject listings:

- Urine and Pregnancy Test Results (positive or negative)
- HSV Antibody Assay
- Collagen VII Antibody Assay
- Viral Shedding
- Infectivity

9 Other Relevant Data Analyses/Summaries

9.1 Protocol Deviations

A listing of all protocol deviations will be provided. Deviations will also be reviewed by the Sponsor and categorized into general categories such as major and minor. Review of protocol deviations will be conducted and finalized prior to unblinding the database. The number of subjects with at least one protocol deviation, the number of subjects with a minor protocol deviation, the number of subjects with a major protocol deviation, and the number of subjects with at least one major deviation for the ITT population. A major deviation is defined as one that potentially affects the efficacy and/or safety analyses.

9.2 Medical/Procedural History

Medical/procedural history is collected during Screening or Visit 1 (Week 1). Medical/procedural history data will be summarized by MedDRA system organ class and preferred term, and a subject listing will be provided.

9.3 Prior and Concomitant Medications

The prior and concomitant medications will be summarized and listed. Medications will be coded with WHO Drug and categorized as either prior medications (any medication that was started before the first application of B-VEC), or concomitant medications (medication continued or newly started on or after the date of first application of B-VEC). A subject listing also will be provided for all prior and concomitant medications.

10 References

Schafer, J.L. (1997) Analysis of Incomplete Multivariate Data. London: Chapman and Hall, p.115.

11 Appendices

[Appendix 1: Schedule of Assessments and Procedures per Visit](#)

[Appendix 2: Adverse Event Date Imputations](#)

Appendix 1: Schedule of Assessments and Procedures per Visit

Study Day	Randomized-Double Blinded Placebo-Controlled Treatment Period								Safety Follow-up/ET
	Screening ¹	Week 1	Week 2 -21	Week 22	Week 23	Week 24	Week 25	Week 26	30 days after last dose
Daily Visit Window	-60 to 0	na	± 3 days						± 4 days
Visit	Screening	1	2-21	22	23	24	25	26	SFU
Obtain Consent / Assent	X	X ²							
Inclusion/Exclusion Criteria		X							
Demographics	X	X ²							
Medical History	X	X ²							
Genetic Testing	X ¹								
Wound Selection		X							
Wound randomization ³		X							
Pain Assessment- Wound Pair ⁴		X		X		X		X	
Quality of Life Questionnaire (EQ-5D) ⁵		X						X	
Skindex Questionnaire ⁵		X						X	
Imaging ⁶		X	X	X	X	X	X	X	X
Assessment of Wound Closure ⁷		X	X	X	X	X	X	X	
Swabs for Viral Shedding/Infectivity ⁸		X	X	X	X	X	X	X	
Swabs for Viral Shedding on Dressing Returned ⁹			X						
Obtain Consent / Assent	X	X ²							
Inclusion/Exclusion Criteria		X							
Demographics	X	X ²							
Medical History	X	X ²							
Genetic Testing	X ¹								
Wound Selection		X							
Wound randomization ³		X							
Pain Assessment- Wound Pair ⁴		X		X		X		X	
Quality of Life Questionnaire (EQ-5D) ⁵		X						X	
Skindex Questionnaire ⁵		X						X	
Imaging ⁶		X	X	X	X	X	X	X	X
Assessment of Wound Closure ⁷		X	X	X	X	X	X	X	
Swabs for Viral Shedding/Infectivity ⁸		X	X	X	X	X	X	X	
Swabs for Viral Shedding on Dressing Returned ⁹			X						

- 1 If genetic testing is required, this test may occur up to 60 days prior to the other screening procedures, following subject consent/assent. Genetic testing may take 6-8 weeks to obtain results.
- 2 Informed consent/assent, demographics, medical/ procedural history, urine (if male) and blood specimens will not be re-collected, if collected at a Screening visit.
- 3 The matched primary wound pair will be randomized.
- 4 Pain questionnaires are to be completed during the dressing change of the individual matched wounds. If subject is 6 years of age or older, they will be asked to complete the VAS questionnaire for matched wounds during the dressing change. If younger than 6 years of age, their parent/caregiver will be administered the FLACC-R questionnaire for the matched wounds during the dressing change (Refer to section 6.2).
- 5 Both the Quality of Life (EQ-5D) and Skindex Questionnaires will be administered to subjects 12 years of age and older at the time of consent. Questionnaires may be administered for the subject to complete after the visit and bring back at the next scheduled visit.
- 6 Images will be collected on both closed and open wounds. Image in the same order and orientation at each visit prior to IP application.
- 7 Primary wound closure assessments will be evaluated by the Investigator only at Weeks 8, 10 12, 22 24 and 26. Secondary wound closure is assessed weekly, to determine if a new wound may be selected to receive treatment, if the originally selected area and its neighboring wound/s has closed, as applicable.
- 8 Viral shedding and infectivity swabs will be collected from the primary matched wounds only and will be collected whether or not the wound is open or closed.
- 9 Subjects are required to bring the study visit wound dressing back to the site. Primary wounds will be separately bagged. Secondary wound dressing may be bagged together. Once returned to the site, viral shedding swabs will be collected for all Primary Wounds dressings that came into contact with the subject's skin. Attempt collection of (4) four consecutive VS dressing returns, if unable, collect at least (4) four dressing VS per subject. Once four (4) VS samples have been collected from the Primary Wound Pair, all dressing may be bagged together and returned to the site for disposal and specimen collection will be discontinued.

Study Day	Randomized-Double Blinded Placebo-Controlled Treatment Period								Safety Follow-up/ET
	Screening ¹	Week 1	Week 2 -21	Week 22	Week 23	Week 24	Week 25	Week 26	30 days after last dose
Daily Visit Window	-60 to 0	na	± 3 days						± 4 days
Visit	Screening	1	2-21	22	23	24	25	26	SFU
Physical Exam ¹⁰		complete						Abbrev.	Abbrev
Treatment and Procedure Review ¹¹	X	X	X	X	X	X	X	X	X
Medication Review ¹¹	X	X	X	X	X	X	X	X	X
AE and SAE Review		X	X	X	X	X	X	X	X
Vital Signs ¹²		X	X				X		X
Urine Pregnancy Test ^{13,14}		X						X	
Urine for Viral Shedding ¹⁵	X	X ²						X	
CMP w/Direct Bilirubin ¹⁵	X	X ²						X	
CBC/Diff ¹⁵	X	X ²						X	
COL7 & HSV Serum ADA ¹⁵	X	X ²						X	
Whole Blood Viral Shedding ¹⁵	X	X ²						X	
Investigational Product (IP) Administration ¹⁶		X	X	X	X	X	X	X	
Roll-over to LTFU or OLE Protocol ¹⁷									X

¹⁰ The Physical examination is described in section 6.3

¹¹ All medication taken 3 months prior to Screening/Visit 1 through the end of the study will be recorded as well as all applicable procedures and treatments within the last 3 months to Screening/Visit 1.

¹² On days in which both vitals and blood draw occur, attempt vitals prior to the blood draw. Vitals are collected every 5 visits (i.e. Visit 1; 5; 9; 13; 17; 21; 25; SFU/ET). Vitals may be obtained more frequently as determined by the Investigator.

¹³ A urine pregnancy test will be completed on all women of childbearing potential prior to blood collection and drug administration, as determined by the Investigator.

¹⁴ For Subjects with history of genitourinary involvement, including painful urination due to the underlying disease and or Subjects who are 4 years of age and younger, are not required to provide a urine sample, as determined by the Investigator. Documentation must be recorded on the CRF and listed in Medical History.

¹⁵ Labs will be attempted, unless per the discretion of the Investigator, it is not in the best interest of the subject. If labs are attempted and not obtained, documentation will be noted in the study visit. Furthermore, if labs are not attempted, justification must be recorded in the study visit. The Investigator must determine clinical significance for out-of-range values.

¹⁶ Conduct all other study visit procedures prior to B-VEC and placebo administration. Matched Wounds: IP will be applied to wounds that are open. If a matched wound and neighboring wound is closed, no IP will be applied and application will be reinitiated once the wound reopens at a scheduled visit, as determined by the Investigator. Secondary Wounds: IP will only be applied to open wounds as determined by the Investigator, not to exceed the Remaining Weekly Dose. IP may be applied to immediate neighboring wounds. Up to four (4) unmatched Secondary Wounds may be selected to receive open-label B-VEC during the study treatment. Trace the area that is receiving treatment (including the neighboring wounds). Neighboring wounds are defined as wounds approximately 2-3cm away from the original matched and unmatched (Primary and Secondary) wound.

¹⁷ At the Safety Follow-up (30 days ± 4 days) following the last dose of B-VEC, subjects may roll over into an OLE protocol or will be asked to roll over into a LTFU protocol

